#### 4.1 Exposure to Partners During the Study

There is a unknown risk of drug exposure through the ejaculate (which also applies to vasectomised males) that might be harmful to the sexual partners, including pregnant partners, of male subjects. Although the risks of this are at present unknown this should be carefully explained to all male patients taking Coversin and they should be advised to use barrier contraception until reproductive toxicity data become available.

#### 4.2 Sperm Donation

Male subjects should not donate sperm for the duration of the study and for at least 90 days after the last day of Coversin administration.

## 5.0 SUBJECT WITHDRAWAL CRITERIA

Subjects may be withdrawn from the trial in the following circumstances:

• An adverse event graded serious or severe which in the opinion of the PI is possibly, probably or definitely related to administration of the trial drug.

- Any other reason for which, in the opinion of the PI it would not be in the best interests of the subject to remain in the trial.
- At the request of the subject for any reason.
- Non-compliance or behaviour not compatible with the proper conduct of the trial.

Appropriate clinical and serological data will be entered in the CRFs. In addition the Subject Withdrawal page of the CRFs will be completed. All data that would normally have been entered on the final day of dosing will be collected and entered together with such additional data as the PI considers clinically necessary to ensure the subject's safety or to elucidate the nature of the AE (e.g. special tests, X Rays, scans, photographs etc.)

#### 6.0 TRIAL PROCEDURE

The trial will comprise an open label, non-comparative study of minimally 1 patient and maximally 6 patients with PNH and known resistance to Eculizumab, who meet the inclusion and exclusion criteria (see below). Patients agreeing to participate in the trial will be admitted to the hospital for a minimum of 2 days for initiation of Coversin treatment, for clinical observation and for bloodsampling (PK/PD). Treatment will be continued on an out-patient basis with daily visits until stabilization or adjustment of dose.

Patients deemed capable of self-administration will be taught how to calculate and draw up the appropriate volume of solution for injection and how to inject subcutaneously. They will also be taught how to store and thaw Coversin prior to injection.

For Patients deemed not capable of self administration, alternative facilities for administration at home will be sought (General Physician or suitably qualified home care nurse).

Only if, in the opinion of the PI, the patient is capable of self injecting the correct dose of Coversin or adequate alternative facilities existfor safety monitoring and dosing supervision, treatment will be transferred to admisitration at home.

If not already immunised against *Neisseria sp.* immunisation and prophylactic antibiotics will be administered as set out in Section 10 below. Nose and throat swabs will be taken although growth of *Neisseria* species will not be grounds for exclusion but will prompt particular vigilance on the part of the PI.

The ablating dose will be divided between as many injection sites as are necessary to avoid injection of >1.2mL of Coversin solution for injection. These sites may be chosen from the deltoid regions, the anterior abdominal region or the anterior femoral regions. The injection sites used will be recorded in the patient notes and will be inspected at 24 hour intervals for 5 days for injection site reactions.

Doses of Coversin will be given at the same time each day, preferably between 6 and 8am. The time of each dose will be recorded in the CRFs. Patients self-administering Coversin will use suitable sites on the anterior femoral and anterior abdominal regions and the site, date and time of injection will be entered on the appropriate CRF sheet (patient diary) and be initialled by the supervising nurse.

All patients will return to the hospital out patient clinic for follow-up at a minimum of monthly intervals according to the schedule in appendix 1.

Blood and urine samples will be taken from all patients according the schedule on appendix 1.

Patients who have satisfactorily mastered the technique of self-administration of Coversin may be discharged home when considered appropriate to do so by the PI providing that adequate arrangements for daily pre-dose blood sampling and sample handling for CH50 samples have been arranged (see below).

All patients will be followed up at a minimum of monthly intervals by the PI. If at the 6 month follow-up the patient wishes to continue Coversin treatment and if the PI is satisfied as to the suitability of Coversin treatment, the patient may be transferred to the long-term follow-up protocol.

It is expected that the majority of patients will respond to an ablating dose of 0.57mg/kg followed by a daily maintenance dose of 25% of the ablating dose.

On a per patient basis this will be adjusted as necessary on the basis of clinical response and CH50 assay. The protocol allows for a flexible, tailored dose adaptation on day 7 and any subsequent follow-up. in patients who are not adequately controlled as is outlined below ..

If patients are not adequately controlled at the first (7 day) or subsequent follow up either of three options may be followed:

Patient will be reinduced with an identical ablating dose (0.57 mg/kg) and /or the maintenance dose may be increased with one step at the time for a maximum of 2

times according to the below schedule of increments . Each incremental dose level must be given for a minimum of 4 days.

The definition of adequately controlled coversin treatment is:

LDH <1.5xULN AND CH50 <10% of baseline.

It is expected that this adequate control is achieved at day 5.

If a recent CH50 result is not available at the time of assessment then the PI will make a decision on clinical grounds alone on the adequacy or otherwise of disease control.

If adequate control is not achieved on day 5 of maintenance therapy at the standard dose level (and day 5 of increment dose levels if applicable) the following dose adaptation will take place:

- If CH50  $\leq 10\%$  and LDH is reducing but still  $\geq 1.5xULN$ , treatment at the same maintenance dose level is continued for another week.
- If LDH is decreasing and if CH50 is between 50 and 10% of baseline, the maintenance dose may be increased according to the schedule of increments of maintenance dose shown below.
- If LDH is not reducing and CH50 is >50% of baseline the patient must either be discontinued from the trial and switched to alternative therapy or must be readmitted to hospital for dose stabilisation following another ablating dose (0.57mg/kg) of Coversin. In either case the findings and course of action must be discussed by a Trial Steering Committee comprised of, at minimum, the PI, and the Medical Director of the Sponsor company.

The schedule of increments for the maintenance dose is as follows:

Ablating dose	First maintenance	Second mainte-	Third mainte-
	dose level	nance dose level	nance dose level
0.57 mg/kg	0.14 mg/kg	0.29 mg/kg	0.57 mg/kg

Within each patient the first incremented maintenance dose should be given at 24 hour intervals for at least 4 days until steady state is reached and at that point a CH50 assay should be performed. If the CH50 is not  $\leq 10\%$  of baseline (adjusted to 100%) then the next incremental dose (Second maintenance dose level should be given for at least another 4 days before switching to the Third maintenance dose level. If at any

stage the CH50 is >50% of baseline another ablating dose should be given before using the next incremental dose.

[figure not shown]
Blood samples and timing is shown in Appendix 1. Samples for CH50, antibodies and drug level should be processed as shown in Section 20 and sent to the Akari Therapeutics Plc complement laboratory for assaying. All other laboratory tests should be done locally in the PI's hospital laboratory.

If an ablating dose is repeated , PK/PD and other assessment will be performed as indicated in Appendix 1 at 1hr, day 2 and day 5.

At increments of the maintenance dose PK and PD and other assessments are repeated at day 5 as indicated in Appendix 1.

Extra samples for PK/PD may be taken at the discretion of the investigators during illness or infection.

#### Flow chart: Schedule of Procedures and Visits

The trial will continue for 6 months or until it has been decided by the PI in consultation with the Sponsor Company that further Coversin treatment is futile or not in the patient's best interests. If the patient is satisfactorily controlled and wishes to continue on Coversin he/she will be permitted to enter the long-term follow-up study. Drug will, if necessary, be supplied free of charge by the Sponsor until it is approved for this indication and reimbursed through the normal channels.

#### 6.1 Endpoints

Primary Efficacy Endpoint:

• Significant reduction in mean serum LDH from Day 0 (pre-dose) to Day 28 (AUC)

Secondary Efficacy Endpoints:

- Change in LDH from Day 0 (pre-dose) at monthly intervals after Day 28
- Change in proportion of PNH clone Day 0 Day 90
- Change in mean Hb Day 0 Day 90
- Change in mean Hp Day 0 Day 90
- Change in FACIT score Day 0 day 28- Day 90 Day 180
- Change in EORTC QLQ C30 score Day 0 -Day 28-Day 90 Day 180

Safety Endpoints:

- Frequency, type and relationship to treatment of AEs and SAEs
- Out of range laboratory parameters (haematology and chemistry)
- Vital signs
- ECG abnormalities Day 0 Day 90

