#### 3.1 Endpoints

Safety:

- Frequency, type and relationship to treatment of AEs and SAEs
- Out of range laboratory parameters (haematology and chemistry)
- Vital signs
- ECG abnormalities Day 0 Day 90

Primary efficacy endpoint:

• Serum lactic dehydrogenase (LDH) AUC from Day 0 to Day 28 compared with 28 days pre-treatment

Secondary efficacy endpoints:

- Haemoglobin at Day 28 and day 90 and Day 180, absolute and change from baseline
- LDH at days 90 and 180
- Haptoglobin at day 28, day 90 and day 180, absolute and change from baseline
- Dependency on blood transfusion
- Quality of Life at days assessed by the FACIT and EORTC QL-C30 instruments compared to Day 0, day 28, 90 and 180

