#### **13 STATISTICS**

#### **13.1** Statistical Methods

The statistical approach taken will depend on the number of patients recruited.

If less than 4 patients are recruited, each patient will be analysed separately. Changes in the primary efficacy outcome during the period Day 0 to Day 28 will be analysed using linear regression using all measurements in the analysis. Secondary efficacy outcomes measured multiple times will be analysed in an equivalent manner.

If 4 or more patients are recruited, the patients will be analysed as a single group. Differences between specific timepoints (e.g. Day 0 and Day 28) for the primary and secondary efficacy endpoints will be performed using the paired t-test.

Additionally the change in the primary efficacy outcome over time will also be examined using all measurements. Mixed model will be used to allow for repeat measurements from the same patients, with the patient considered as a random effect.

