#### **13.3** Significance Level

For all comparisons p < 0.05 will be considered significant.

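### LDH changes after Day 28 are measured from the Day 0 value alone, although Section 3.1 already needs a 28-day pre-treatment LDH series that would give a steadier baseline

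*Combined protocol and SAP*

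**What the plan says.** Section 6.1 lists as a secondary endpoint "Change in LDH from Day 0 (pre-dose) at monthly intervals after Day 28". Section 3.1 gives the later LDH endpoint as "LDH at days 90 and 180" and names no reference value.

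For the primary endpoint, Section 3.1 specifies "Serum lactic dehydrogenase (LDH) AUC from Day 0 to Day 28 compared with 28 days pre-treatment". An area under the curve over that window needs at least two readings; their number and timing are not given. Section 6.1 words the primary endpoint from Day 0 and mentions no pre-treatment window.

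Section 13.1 sets the analysis by enrolment. With 4 or more patients, "Differences between specific timepoints (e.g. Day 0 and Day 28) for the primary and secondary efficacy endpoints will be performed using the paired t-test". With fewer than 4, each patient gets a linear regression on all measurements, and "Secondary efficacy outcomes measured multiple times will be analysed in an equivalent manner". Section 13.3 adds: "For all comparisons p < 0.05 will be considered significant".

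The synopsis requires LDH of at least 1.5 times the upper limit of normal (ULN) at entry. It does not say when the qualifying sample is taken, and Section 9.1 omits the criterion. The list of prohibited medications asks for eculizumab to stop ideally 2 or more weeks before Coversin, which is shorter than 28 days.

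**The concern.** The trial is open label with no control arm and at most 6 patients, so each patient's own baseline is the only comparator for LDH control beyond Day 28. If that baseline is one reading, its error goes in full into every monthly change. Precision is lost, and changes at successive months are correlated, so a run of falls carries less evidence than it appears to. Enrolment cannot recover the lost precision, whereas averaging readings that Section 3.1 already calls for would recover part of it.

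**Working it through.** The documents give no power, effect size or LDH variability for this endpoint, so there is no stated figure to reproduce.

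**From the documents:** Day 0 reference (6.1); a pre-treatment LDH series (3.1); paired t-test at n of 4 or more (13.1); up to 6 patients (13.2); p < 0.05 (13.3), taken as two-sided; 6 months of treatment, hence about five monthly changes after Day 28.

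**Assumed:** k pre-treatment readings, k = 2 to 4; the same within-patient SD s for every reading; correlation r between baseline readings, 0 to 0.7; within-patient CV 20%; between-patient SD of the true log response 0.1 or 0.2.

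**1. Error of one change.** The variance is s²(1 + 1/k) for independent readings. At k = 1 it is 2s², half of it from Day 0. The SE relative to a single baseline is √[(1 + 1/k)/2]:
- k = 2: 0.866 (13% lower)
- k = 3: 0.816 (18% lower)
- k = 4: 0.791 (21% lower)

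With correlated baseline readings, replace 1/k by [1 + (k−1)r]/k. At k = 4 the ratio is 0.859, 0.901 and 0.942 for r = 0.3, 0.5 and 0.7, that is 14%, 10% and 6% lower.

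**2. Shared error.** The correlation between two monthly changes is (1/k)/(1 + 1/k): 0.50 at k = 1, 0.33 at k = 2 and 0.20 at k = 4. With no true change and one Day 0 reading, all five changes are falls exactly when Day 0 is the highest of six exchangeable readings, a chance of 1/6 = 17%. By symmetry, all five are rises with the same chance. Simulation gives 11% at k = 2 and 8% at k = 4. Independent changes would give 1/32 = 3%.

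**3. Power of the paired t-test** (log scale, noncentral t). s² = ln(1.04) = 0.0392. For a 30% fall, δ = −ln 0.7 = 0.357. SD = √[(1 + 1/k)s² + 0.1²]; noncentrality = δ√n/SD. At n = 6:

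| Baseline | SD | Noncentrality | Power |
|---|---|---|---|
| k = 1 | 0.297 | 2.94 | 65% |
| k = 2 | 0.262 | 3.33 | 76% |
| k = 4 | 0.243 | 3.60 | 82% |
| k = 4, r = 0.5 | 0.272 | 3.22 | 73% |

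At n = 4, power goes from 38% to 52% (k = 4), or to 44% with r = 0.5. With response SD 0.2, n = 6 and k = 4, it goes from 53% to 65%.

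Section 6.0 defines adequate control partly as LDH below 1.5 times ULN, so a patient entering at 3 times ULN must roughly halve. For a 50% fall (δ = 0.693) at n = 6, a single Day 0 reading already gives 99% power (response SD 0.1) or 97% (SD 0.2).

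**4. Entry selection.** Suppose the Day 0 sample is also the qualifying sample. For a normal reading with mean m and SD 0.2m, the spurious fall is 1 − m/E[X | X ≥ 1.5]:
- m = 1.5: 1 − 1.5/1.739 = 14%
- m = 2: 1 − 2/2.082 = 4%
- m = 3: 1 − 3/3.011 = 0.4%

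The 14% puts every patient's true LDH exactly at the cut. If true values vary between patients (log-SD 0.5, assumed), the fall is about 6%, 4% and 0.2% at medians of 1.5, 2 and 5 times ULN. If the qualifying sample is separate from Day 0, the Day 0 reference carries no such bias. Averaging that screening sample into a four-reading baseline would then create one, of 0.2% to 1.9% at a median of 2 times ULN for CV 10% to 30%.

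**5. Fewer than 4 patients.** In a regression on Days 0, 28, 60, 90, 120, 150 and 180, Day 0 has leverage 0.46 (average 2/7 = 0.29). It is influential but not the sole reference.

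**The case against.** The case for leaving the text alone has real force. Pre-dose Day 0 is a coherent reference and the reading closest to the start of treatment. This is a secondary endpoint in a study whose primary objective is safety, and the synopsis promises only descriptive statistics. The number of pre-treatment readings is unknown. Appendix 1, which sets the sampling times, is not in the supplied text, so repeat Day 0 sampling cannot be ruled out. A short washout could leave only one or two comparable readings, and correlation between readings shrinks the gain. Below 4 patients the regression already uses all measurements. All of this stands and limits the size of the point. It does not reverse the direction: with equally variable readings, a mean of several is never less precise than one.

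Two stronger readings are tempting. A reader might infer that the single Day 0 value biases the later changes towards a fall. The documents do not support that: no section says Day 0 is the qualifying sample, and without selection the error is symmetric. A reader might also infer that the plan counts successive monthly falls as separate confirmation. No section does so.

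**Conclusion.** The point holds as one of precision and clarity. The single Day 0 reference gives away information that Section 3.1 already calls for, and it links all the monthly changes. It matters mainly for descriptive changes and for the paired analysis with 4 or more patients; with fewer, the gain is smaller. For moderate falls at n = 6, power would rise by about 8 to 17 percentage points (65% to between 73% and 82%). For a halving of LDH there is almost nothing left to gain at that sample size. These figures depend on the assumed CV, response SD, number of readings and correlation. A systematic bias towards a fall remains conditional on two things: Day 0 being the qualifying sample, and LDH lying near 1.5 times ULN. The change is worth making before data are seen, as a moderate improvement to a secondary endpoint.

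**What to change.** In Sections 6.1 and 13.1, define baseline for all LDH changes after Day 28 as the mean of the pre-treatment readings used for Section 3.1, including Day 0 (geometric mean if analysed on the log scale). Restrict it to readings with the same eculizumab status as Day 0, and exclude the reading used to qualify on LDH. Say which sample that is. If Day 0 is the only reading that meets these conditions, use it. Report the change from the single Day 0 value as a sensitivity result.

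The cost is wording in two sections and one extra column of results. No samples are added, provided the Section 3.1 series is collected as worded; check this against Appendix 1 and settle the difference between Sections 3.1 and 6.1 on the pre-treatment window. The small downside is that some patients will have few eligible readings and so gain little.

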#### 6.2 Description of Trial Treatments, Dosage and Dosage Regimens

Coversin for subcutaneous injection will be supplied initially as vials of frozen solution, each 2mL vial containing 1.2mL of 7.2mg/mL solution. Vials should be stored frozen at  $-20^{\circ}$ C until between 12 and 24 hours of use when they should be allowed to thaw at ambient or refrigerated (2 – 6°C) temperature. Ideally they should be thawed overnight in refrigerated conditions.

Following the initial batch for use in the first patient treated under this protocol it is likely that all future batches will be supplied as lyophilised powder 15mg in 5mL glass vials. Until reconstituted it can be stored at ambient temperature for the duration allowed by the expiry date printed on the label. It will be reconstituted within 6 hours of administration with 0.5mL of sterile water for injection to form a solution of 30mg/mL concentration. After injection of

sterile water into the Coversin vial it should be shaken a few times until no particulate matter remains. After reconstitution vials should be stored between 2 and 6°C until used and in any case for no longer than 24 hours.

Following the switch to lyophilised powder the maintenance dose will be changed to a fixed multiple of 15mg (ie 15, 30 or 60mg) which will be the next dose above the dose that the patient is being maintained on. Thereafter the first ablating dose in all future patients treated under this protocol will be 60mg (2mL) which will divided between two injection sites.

After the first, ablating, dose all subjects will receive fixed daily maintenance doses for the remainder of the trial. The size of the fixed maintenance dose will be determined by the results achieved in the first patient treated under this protocol. As mentioned above there will be some flexibility to allow for adjustment of dose in individual patients if they do not appear to be responding adequately but the overall aim will be to find a fixed dose that will maintain full complement inhibition in all patients treated.

All doses should be given at the same time each day, ideally between 6 and 8 am. Blood samples should be taken immediately pre-dose or as shown in appendix 1.

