## **Protocol synopsis**

	Exclusion Criteria:		
	• Pregnancy (females)		
	• Known allergy to ticks or severe reaction to arthropod venom (e.g. bee or wasp venom)		
	• Failure to satisfy the PI of fitness to participate for any other reason		
Treatment Regimen:	Single ablating dose of 0.57mg/kg per subject followed by daily maintenance doses. The initial maintenance dose will be 25% of the ablating dose. If this is insufficient to maintain complement activity at $\leq 10\%$ of baseline (pre-treatment) level after 5 days of treatment the daily maintenance dose will be increased by doubling until that level of inhibition is achieved. In the event of 100% inhibition being achieved the dose may be titrated downwards at the PI's discretion until a satisfactory clinical result is obtained. If at any point in treatment complement activity (CH50) is 50% of baseline or more a further ablating dose of 0.57mg/kg should be given. An increased daily maintenance dose may be required in the event of intercurrent infection or illness. CH50 level should be checked in the event of deteriorating clinical response manifested by rising serum LDH.		
Duration of Treatment:	Patients will undergo an initial period of 6 months treatment according to this protocol. At the expiry of this period, and on the recommendation of the PI, patients will have the option of remaining on long-term Coversin therapy and will enter the long term follow-up study.		
Endpoints:	Efficacy Endpoints:		
	Primary: Reduction in serum LDH from day 0 – Day 28		
	Secondary: Hb, haptoglobin, Fatigue (FACIT), Quality of Life (EORTC QL-C30), PNH RBC clone size, Transfusion requirement		
	Safety Endpoints:		
	Adverse events, ECG, Laboratory results, Vital signs.		
Statistical Methods:	Descriptive statistics		

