#### 3.0 TRIAL DESIGN

Treatment with Coversin comprises an ablating dose on day 1 and daily maintenance treatment from day 2 onwards. Calculated according to body weight, the ablating dose will be 0.57mg/kg. Thereafter the daily repeat maintenance dose will be titrated according to clinical response and complement inhibition as determined by CH50 ELISA. The initial daily maintenance dose will be 25% of the ablating dose (0.14 mg/kg) and this will be adjusted up or down if necessary once steady state is reached (5 days). This is further explained in chapter 6, TRIAL PROCEDURE .

In order to mitigate the risk of infection by *Neisseria sp* all subjects or patients taking part in the trial will be carefully instructed about precautions to be taken in case of actual or suspected infection. Patients may either be given permanent antibiotic prophylaxis (oral penicillin daily) or be provided with high dose ciprofloxacin and instructed to immediately commence taking it in the event of a suspected infection. In the latter case they will also be told to make immediate contact with the PI or her deputy. In addition all patients will receive immunisation with quadrivalent meningoccal vaccine Anti meningococcal B vaccine has recently been developed and will be given once approved in the country where the patient is treated. Vaccination against meningococci typ ACW135Y is required at the start of the study. Should the first vaccination take place  $\leq 14$  days of commencement of Coversin, then the patient must take high dose antibiotic for the first 2 weeks. This will generally be ciprofloxacin daily (2x 750mg orally, until 2 weeks have elapsed since first vaccination) or alternative antibiotic treatment directed against meningococci.

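### Two unreconciled rules set the starting maintenance dose of patients 2 to 6: they agree if patient 1 is controlled on the first level, but can differ up to 4-fold if not

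*Combined protocol and SAP*

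**What the plan says.** **Rule A: a set starting fraction, then titration within the patient.** The synopsis states: "The initial maintenance dose will be 25% of the ablating dose". Section 3.0 repeats it with a figure: "The initial daily maintenance dose will be 25% of the ablating dose (0.14 mg/kg". Neither place limits the rule to the first patient. Section 6.0 adds an expectation, "It is expected that the majority of patients will respond to an ablating dose of 0.57mg/kg followed by a daily maintenance dose of 25" per cent of the ablating dose. It then moves a patient up a three-level schedule (0.14, 0.29 and 0.57 mg/kg) according to that patient's own CH50 and LDH.

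**Rule B: a fixed dose taken from patient 1.** Section 6.2 states: "After the first, ablating, dose all subjects will receive fixed daily maintenance doses for the remainder of the trial". It continues: "The size of the fixed maintenance dose will be determined by the results achieved in the first patient treated under this protocol". On the switch to lyophilised product, "the maintenance dose will be changed to a fixed multiple of 15mg (ie 15, 30 or 60mg"); a switched patient takes the smallest of these that exceeds his or her current dose. For later patients, "the first ablating dose in all future patients treated under this protocol will be 60mg (2mL"). Section 6.2 keeps some room to adjust the dose of an individual who does not respond adequately.

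**Context.** Section 1.4 explains that patient 1 is dosed by weight because supply is limited at first, and that this patient and others may later move to fixed dosing. It foresees maintenance at 25 to 50% of a 60 mg dose. Section 6.2 calls the lyophilised supply likely, not certain.

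**The concern.** The two rules take the starting level of a later patient from different sources. Under Rule A the source is a set fraction, and any increase follows from that patient's own response. Under Rule B it is the outcome in someone else. If patient 1 ends above the first level, both cannot be followed, and two investigators reading the same protocol could start the same patient differently.

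Section 6.2 also does not say which of patient 1's results counts (for example the level at Day 5, at Day 28 or at six months), how that result becomes a dose, or what happens if patient 2 enrols before it is known.

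The conflict is about the starting level. It is separate from the change from mg/kg to fixed mg, because 25% of 60 mg is itself one of the permitted fixed doses. Both rules could be written in mg and still disagree.

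Two things depend on it. Early exposure differs between the readings, and safety is the primary objective in the synopsis. The primary efficacy endpoint is LDH over Day 0 to Day 28, and with four or more patients Section 13.1 analyses everyone as one group, with no mention of dose level.

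**Working it through.** **Inputs**
- Ablating dose 0.57 mg/kg; maintenance levels 0.14, 0.29 and 0.57 mg/kg (Section 6.0, schedule of increments).
- Fixed maintenance doses 15, 30 and 60 mg; fixed ablating dose 60 mg (Section 6.2).
- Body weight 50 to 100 kg (Sections 9.1 and 9.2).
- One to six patients (Section 1.6); pooling from four (Section 13.1).

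**Step 1. Reproduce the plan's figures.** 0.25 × 0.57 = 0.1425, stated as 0.14. 0.50 × 0.57 = 0.285, stated as 0.29. 1.00 × 0.57 = 0.57, as stated. The three levels are therefore 25%, 50% and 100% of the ablating dose.

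**Step 2. Rule A for a later patient.** 0.25 × 60 mg = 15 mg daily.

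**Step 3. Rule B for a later patient.** The plan gives no formula. I assume that patient 1's level is carried over by the conversion in Section 6.2 (the next fixed dose above the current one), which the text states only for a patient being switched. The weight that matters here is patient 1's.

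| Patient 1 controlled on | Patient 1's daily dose, 50 to 100 kg | Next fixed dose above | Ratio to 15 mg |
|---|---|---|---|
| Level 1, 0.14 mg/kg | 7 to 14 mg | 15 mg at every weight | 1 |
| Level 2, 0.29 mg/kg | 14.5 to 29 mg | 30 mg above about 51.7 kg (15/0.29); 15 mg below | up to 30/15 = 2 |
| Level 3, 0.57 mg/kg | 28.5 to 57 mg | 60 mg above about 52.6 kg (30/0.57); 30 mg below | up to 60/15 = 4 |

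The range foreseen in Section 1.4, 25 to 50% of 60 mg, is 15 to 30 mg, so at most 2-fold.

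If Rule A is read as 0.14 mg/kg for the later patient, it gives 7 to 14 mg, and 60 mg is 60/14 = 4.29 to 60/7 = 8.57 times that. Those ratios include the change from weight-based to fixed dosing, so I do not use them as the size of this point.

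**Step 4. Reach within the trial.** Patient 1 starts under Rule A. With six patients, 6 − 1 = 5 could start under Rule B.

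**Step 5. Reach within the endpoint window.** Section 6.0 requires at least 4 days on a level before the next. A patient who climbs from level 1 to level 3 spends at least 4 + 4 = 8 of the 28 days below the level at which another patient could begin under Rule B.

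**The case against.** The best defence is that Sections 1.1, 1.4 and 6.2 describe two phases: weight-based dosing for patient 1 while supply is short, then fixed dosing. On that reading Section 6.2 describes the later phase and does not compete with the 25% start. In the case that Section 6.0 expects, most patients are controlled at 25% and both rules give 15 mg. Titration also means that the Day 0 to 28 LDH can mix dose levels under either rule.

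All of this reduces the size of the point. It does not remove the gap: the two-phase account explains why dosing becomes fixed, but not which rule sets the level at which patients 2 to 6 begin. The synopsis and Section 3.0 carry no limit to a first phase.

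A reader might infer more than the documents support:
- *That Objective 2 may never be tested on the stated regimen.* Patient 1 starts at 25%, and with fewer than four patients each is analysed separately. The regimen in Section 2.0 is dosed by weight and, in Sections 3.0 and 6.0, titrated. The objective never names 25%, so a patient moved up a level is still on that regimen.
- *That a 4-fold difference is to be expected.* It needs patient 1 to end on the third level.
- *That patient 1 is a poor guide to later patients.* Any probability for that would be invented. Treating the three levels as equally likely would contradict the expectation in Section 6.0, and it would judge a clinical rule that belongs to the sponsor and investigator.

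**Conclusion.** The inconsistency is real and conditional. Two rules in the current text set the starting maintenance level of patients 2 to 6, and nothing ranks one above the other. In mg the difference is nil if patient 1 is controlled on the first level, up to 2-fold if on the second, and up to 4-fold (60 against 15 mg) if on the third.

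These sizes rest on three assumptions: the 60 mg ablating dose is in use, the lyophilised supply arrives, and patient 1's level is carried over by the conversion in Section 6.2. If they hold and patient 1 ends above the first level, up to five of six patients could start at a level other than the 25% in the synopsis and Section 3.0. That affects the comparison of early safety between patients and the reading of the LDH result pooled from four patients on. No view is taken on which rule or dose is right.

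**What to change.** Reconcile the synopsis, Section 3.0, Section 6.0 and Section 6.2, together with the supply explanation in Section 1.4, so that one rule governs the starting maintenance level of patients 2 to 6. The sponsor and investigator should choose it before patient 1's result is used. If the rule draws on patient 1, the text should say which result counts, when it is read and how it becomes a starting level.

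In Section 13.1, add a listing of each patient's starting maintenance level and level at Day 28 beside the LDH result, so that a pooled figure can be read against the doses given. I would not split the LDH analysis by starting level or limit Objective 2 to patients who began at 25%. With at most six patients a split could leave one against five, and the objective contains no such limit.

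The cost is a wording amendment and one listing. No extra visits, samples or patients are needed.
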